9.2. Analysis approach

Part 1:

The time and motion study will record the number of steps and time taken to administer the correct dosage of artesunate. We will compare median (IQR, ranges) times for 1-step artesunate and conventional artesunate. Analysis of other endpoints will be described in a Statistical Analysis Plan. We assume 1-step parenteral artesunate is bioequivalent to conventional parenteral artesunate. A brief overview is given below.

9.2.1 General Analysis Strategy

The principle of intention to treat (ITT) will be the main strategy of analysis for the primary outcome. These analyses will be conducted on all patients assigned to the treatment groups as randomised. Any patients subsequently found not to be eligible during the trial or that did not receive a full course of study drug will be included in these analyses. Per Protocol (PP) analysis will be conducted to examine robustness of ITT results. This will be a form of sensitivity analysis to the intention to treatment analysis principle. In the PP analyses, all patients wrongly included in the study based on the inclusion/exclusion criteria will be excluded from analyses.

The cost analysis of 1-step parenteral AS will assess health facility-level costs, and health system costs to encompass all costs of a potential change from conventional to 1-step artesunate, including re-training, materials, drug replacement. Unit costs will be assigned to healthcare worker time spent on managing patients with severe malaria (derived from the time and motion surveys). Micro costing will be carried out in each of the sites to estimate the costs of equipment and consumables associated with provision of artesunate with each of the formulations. The resulting labour and consumable mean costs will be compared in patients treated with 1-step vs conventional artesunate formulation.

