6. PROCEDURES

Part 1

A trial nurse will receive all children who could have severe malaria and are potentially eligible to participate in the study and call the attending physician. The diagnosis of *falciparum* malaria will be made by a PfHRP2-based rapid malaria test. If the test is positive, and there is a clinical judgement that the patient has severe disease (according to a check list provided in the Case Report Forms [CRFs]), the patient can be enrolled, provided written informed consent has been obtained and all eligibility confirmed. The screening sequence will differ for patients with hyperparasitaemia only with no symptoms of severe malaria, as their eligibility will be determined when microscopy results are available, if performed.

Once the patient is enrolled, the randomisation deciding the drug allocation will be carried out. This is done in the following way: The next in a series of numerically sequenced envelopes is opened. The envelope will contain the unique participant number. From the moment the envelope is opened the patient is considered in the study whether or not the protocol is followed correctly thereafter. The envelope contains a slip of paper with a treatment box code number. The treatment box with this code number is then opened.

With the help of the study nurse, the attending physician will take the patient's history, and do a physical exam, where the list in the Case Report Forms (CRFs) serves as a guideline. Parameters include basic demographic parameters, questions regarding the previous history and current history, vital signs, coma score, and others. Patient monitoring during admission: to assure the best possible treatment of each study patient the following variables will be monitored based on WHO guidelines²¹

A detailed monitoring sheet will outline the planned observations and their frequency. In case of abnormal findings staff will be trained to repeat the test and to inform the key decision makers regarding the need to change the management of the patient. To help the treating physician, a practical guideline on the treatment of severe malaria (appendix 4) will be provided to all involved physicians.

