2. GENERAL ANALYSIS APPROACH

The principle of intention to treat (ITT) will be the main strategy of analysis for the primary outcome. These analyses will be conducted on all patients assigned to the treatment groups as randomised. Any patients subsequently found not to be eligible during the trial or that did not receive a full course of study drug will be included in these analyses. Per Protocol (PP) analysis will be conducted to examine robustness of ITT results. This will be a form of sensitivity analysis to the intention to treatment analysis principle. In the PP analyses, all patients wrongly included in the study based on the inclusion/exclusion criteria will be excluded from analyses.

The cost analysis of 1-step parenteral AS will assess health facility-level costs, and health system costs to encompass all costs of a potential change from conventional to 1-step artesunate, including re-training, materials, drug replacement. Unit costs will be assigned to healthcare worker time spent on managing patients with severe malaria (derived from the time and motion surveys). Micro costing will be carried out in each of the sites to estimate the costs of equipment and consumables associated with provision of artesunate with each of the formulations. The resulting labour and consumable mean costs will be compared in patients treated with 1-step vs conventional artesunate formulation.

Time from opening box to completed preparation of syringe will be summarised using means and standard deviation for each each arm. Difference in means and the correponding 95% confidence intervals will be reported. We will provide overall comparisons by arm as well as for each site separately. The comparisons will be done for baseline times ans well as for all recorded times. Total cost of consumables in US dollars will be summarised in a similar way. A Student's independent t-test will be used for comparison of means between groups. The Central Limit Theorem justifies the use of the Student's t-test even if the times/costs may not be normally distributed because of the large sample size. However, if the data will be highly skewed, non-parametric tests such as Manny-Whitney (Wilcoxon) U test will be considered. Statistical significance will be declared at 5% significance level.

Data analysis will be performed using Stata 17 or higher, StataCorp, 4905 Lakeway Drive College Station, Texas 77845 USA

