3.4 Fever clearance and parasite clearance during treatment, by treatment allocation

Table 4 Clinical recovery*, fever clearance, and parasite clearance by study arm**

	1-STEP AS N=XXX	2-STEP AS N=XXX	Both groups N=XXX	P- value (2-sided)
Hours to fever clearance, mean (SD) (baseline to start of first 24h period <37.5C; temperature was recorded every 4 hours, until day 2, then 6 hourly)				
DRC	XX.X (X.X)	XX.X (X.X)	XX.X (X.X)	X.XXX
Tanzania	XX.X (X.X)	XX.X (X.X)	XX.X (X.X)	X.XXX
All study sites	XX.X (X.X)	XX.X (X.X)	XX.X (X.X)	X.XXX
Day 3 blood smear still positive, n/N (%)** (taking prior clearance or discharge as negative)				
DRC	XX/XXX (XX)	XX/XXX (XX)	XX/XXX (XX)	X.XXX
Tanzania	XX/XXX (XX)	XX/XXX (XX)	XX/XXX (XX)	X.XXX
All study sites	XX/XXX (XX)	XX/XXX (XX)	XX/XXX (XX)	X.XXX
Hours to tolerate oral medication, mean (SD)* (baseline to start of oral ACT)				
DRC	XX/XXX (XX)	XX/XXX (XX)	XX/XXX (XX)	X.XXX
Tanzania	XX/XXX (XX)	XX/XXX (XX)	XX/XXX (XX)	X.XXX
All study sites	XX/XXX (XX)	XX/XXX (XX)	XX/XXX (XX)	X.XXX
Parasite clearance half-life in hours, mean (SD)** (excluding patients with initial count insufficient to estimate half-life)				
DRC	X.X (X.X)	X.X (X.X)	X.X (X.X)	X.XXX
Tanzania	X.X (X.X)	X.X (X.X)	X.X (X.X)	X.XXX
All study sites	X.X (X.X)	X.X (X.X)	X.X (X.X)	X.XXX

*Protocol recommends patients receive a minimum of 3 doses of injectable artesunate before switch to oral ACT. Patients may vary if discharged before 24 hours, died, or referred.

** Parasite dynamics will be affected by patients who are transfused.

STATISTICAL ANALYSIS PLAN
3.5 Safety assessments and tolerability (Incidence of adverse events and serious adverse events by study arms within the first 28 days)

Safety analyses will be based on the whole population that get administered the study drug. That is, the safety and tolerability data will be pooled from all the sites that received the same antimalarial treatment.

The safety and tolerability of 1-STEP AS versus 2-STEP AS will be assessed by comparing the frequency (%) of adverse events and serious adverse events, with particular attention to the variables listed below, which pertain to severe malaria.

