Safety data will be presented in tabular and/or graphical format and summarized descriptively. Any clinically relevant abnormalities or values of potential clinically concern will be described. Patients will be analysed following the intention to treat analysis. All adverse event summaries will refer to treatment emergent adverse events, i.e. adverse events that newly started or increased in intensity after the study drug administration. Adverse events will be graded according to Common Terminology Criteria for Adverse Events (CTCAE). The safety and tolerability summaries will be presented in table 5.

Table 5 Incidence of adverse events within first 28 days by study arm

	1-STEP AS	2-STEP AS	p-value
Number of subjects	XX	XX	
Serious adverse events (SAEs), n/N, (%)	XX	XX	X.XXX
Possible, probable or definite drug related SAEs, n/N, (%)	X/XX (X.X)	X/XX (X.X)	X.XXX
Neurological sequelae at discharge	X/XX (X.X)	X/XX (X.X)	X.XXX
Neurological sequelae at 28	X/XX (X.X)	X/XX (X.X)	X.XXX
Neurological sequelae persisting at end of follow up	X/XX (X.X)	X/XX (X.X)	X.XXX
Grading of adverse events, n/N, (%)	1-2	3-4	1-2
Symptoms			
Impaired consciousness or unrousable coma, n (%)	X/XX (X.X)	X/XX (X.X)	X/XX (X.X)
Prostration, n (%)	X/XX (X.X)	X/XX (X.X)	X/XX (X.X)
Failure to feed and drink without assistance, n (%)			
Multiple convulsions, n (%)			
Deep breathing, respiratory distress, n (%)	X/XX (X.X)	X/XX (X.X)	X/XX (X.X)
Circulatory collapse or shock, systolic BP < 70 mmHg, n (%)	X/XX (X.X)	X/XX (X.X)	X/XX (X.X)
Clinical jaundice plus evidence of other vital organ dysfunction, n (%)	X/XX (X.X)	X/XX (X.X)	X/XX (X.X)
Haemoglobinuria, n (%)	X/XX (X.X)	X/XX (X.X)	X/XX (X.X)
Suspected pulmonary oedema, n (%)	X/XX (X.X)	X/XX (X.X)	X/XX (X.X)

STATISTICAL ANALYSIS PLAN

	X/XX (X.X)	X/XX (X.X)	X/XX (X.X)	X/XX (X.X)	X.XXX
Renal failure (< 20 ml urine per hour) , n (%)	X/XX (X.X)	X/XX (X.X)	X/XX (X.X)	X/XX (X.X)	X.XXX
Spontaneous bleeding/disseminated intravascular coagulation, n (%)	X/XX (X.X)	X/XX (X.X)	X/XX (X.X)	X/XX (X.X)	X.XXX
Several episodes of vomiting in the preceding 24 hrs, n (%)	X/XX (X.X)	X/XX (X.X)	X/XX (X.X)	X/XX (X.X)	X.XXX
Severe pallor with respiratory distress OR HCT<15% OR hb<5.0g/dl, n (%)	X/XX (X.X)	X/XX (X.X)	X/XX (X.X)	X/XX (X.X)	X.XXX
Total	X/XX (X.X)	X/XX (X.X)	X/XX (X.X)	X/XX (X.X)	X.XXX
Laboratory abnormalities					
Creatinine	X/XX (X.X)	X/XX (X.X)	X/XX (X.X)	X/XX (X.X)	X.XXX
Total bilirubin	X/XX (X.X)	X/XX (X.X)	X/XX (X.X)	X/XX (X.X)	X.XXX

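### The per-protocol set excludes only ineligible children, so it cannot show whether doses prepared with the non-allocated formulation diluted the time difference; the safety grouping also needs one stated rule

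*Protocol*

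**What the plan says.** The main analysis of the primary outcome is ITT: "These analyses will be conducted on all patients assigned to the treatment groups as randomised" (Protocol 9.2.1, repeated in SAP section 2). Protocol section 6 supports this: "From the moment the envelope is opened the patient is considered in the study whether or not the protocol is followed correctly thereafter".

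The role of PP is given in the same two sections: "Per Protocol (PP) analysis will be conducted to examine robustness of ITT results". Its content is one rule: "In the PP analyses, all patients wrongly included in the study based on the inclusion/exclusion criteria will be excluded from analyses". Neither document adds an exclusion for use of the other arm's formulation or for a missing timing.

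On safety, SAP 3.5 opens with "Safety analyses will be based on the whole population that get administered the study drug" and explains it with "That is, the safety and tolerability data will be pooled from all the sites that received the same antimalarial treatment". Further down the same section it says "Patients will be analysed following the intention to treat analysis". Protocol 9.2.4 also takes everyone who was given study drug, but does not say how they are grouped.

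**The concern.** In a non-inferiority comparison, deviations that make the arms more alike can help the claim. A PP analysis is normally added to show whether the ITT result depends on them. The time endpoint here is a stopwatch reading taken while a nurse prepares a vial (Protocol section 6), so the deviation that bears on it most directly is opening the wrong product. The stated PP set leaves such doses in. If ITT and PP agreed, the agreement would say nothing about this kind of dilution.

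The safety wording is a separate and smaller matter that touches only the safety tables. A child randomised but never dosed is in an ITT set and outside a treated set. For a child given the other formulation, the arm is not stated. Both the denominators and the arm assignment in SAP Table 5 are therefore open to choice after the data are seen.

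**Working it through.** **Inputs.** From Protocol 9.1 and SAP 2.2.1: margin 1 minute, SD 2 minutes, one-sided alpha 0.025, power 90%, 85 per arm, and 100 per arm after 15% loss. Assumed, because the documents give no figure: the share c of doses prepared with the non-allocated formulation, taken as 2% to 10%.

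**Step 1: the plan's own figure.** With no true difference, n per arm = 2 × [2 × (1.960 + 1.282) / 1]² = 84.06, rounded up to 85. Then 85 / (1 − 0.15) = 100. Both stated figures reproduce and are not in dispute.

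**Step 2: effect of wrong-formulation doses on the ITT difference.** Let D be the true difference, 1-step minus 2-step. If a share c of one arm gets the other product, the expected difference is D(1 − c). If it happens in both arms, it is D(1 − 2c).

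**Step 3: one-sided error at the margin.** Set D = 1 and use 100 per arm, so SE = 2 × √(2/100) = 0.283. Take the decision rule implied by the sample-size section: the upper 95% limit must lie below 1 minute. Then P(claim) = Φ[(1 − expected difference) / 0.283 − 1.96].

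| c | Expected difference, one arm | Error | Expected difference, both arms | Error |
|---|---|---|---|---|
| 0 | 1.00 | 0.0250 | 1.00 | 0.0250 |
| 2% | 0.98 | 0.0294 | 0.96 | 0.0345 |
| 5% | 0.95 | 0.0373 | 0.90 | 0.0541 |
| 10% | 0.90 | 0.0541 | 0.80 | 0.1051 |

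With 85 per arm, the errors are 0.036 and 0.051 at 5%, and 0.051 and 0.095 at 10%. Mixing two products also widens the within-arm variance, to 4 + c(1 − c). Allowing for this changes little: 0.1051 becomes 0.1037.

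**Step 4: the opposite direction.** If 1-step is truly 1 minute faster (D = −1) and c = 10% in both arms, the expected difference is −0.8. P(claim) = Φ[1.8 / 0.283 − 1.96] = Φ(4.40), which is close to 1. Dilution then understates the benefit and creates no false claim.

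**Step 5: cost of a stricter PP set.** Power at no true difference is Φ[1 / (2 × √(2/n)) − 1.96]: 0.942 at 100 per arm, 0.931 at 95 and 0.918 at 90.

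**Step 6: the safety sentences side by side.** The first says who is included: treated children. The third names ITT, which usually fixes both membership and grouping. The middle sentence, on pooling, can be read as pooling across sites or as grouping by treatment received. No sentence settles the arm for a child given the other product.

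**The case against.** Four counter-arguments deserve weight.

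- **ITT already places these children.** A reader might infer that wrong-formulation doses are not handled at all. The documents do not support that: the ITT rule and the envelope rule keep the child in the randomised arm. What is missing is a sensitivity rule. This stands.
- **Mix-ups should be rare.** A numbered envelope leads to a coded treatment box, study staff give the drug, and an observer is paired with each nurse and starts timing when the pack is opened. If mix-ups occur, the likelier direction is use of the 2-step product in the 1-step arm, because 2-step is current standard care at both sites. That points to the one-arm column. The protocol also expects 1-step to be faster, where Step 4 applies. This stands, and it limits the size of the point.
- **The safety sentences can be reconciled.** A reader might infer that they place wrongly treated children in different arms. Treated children grouped as randomised is a coherent reading, so a contradiction is not proven. The SAP does not state that reading, however, so the ambiguity remains. Safety is exploratory and descriptive, and no primary claim depends on it.
- **A stricter PP set can itself bias.** Excluding faulty preparations would select on something the trial compares, since the protocol's background calls the 2-step procedure error prone. This is right, and the fix below keeps such preparations in.

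Two smaller points are also fair. Eligibility errors are not wholly irrelevant to preparation time, because weight drives dose and the number of vials. And a missing time cannot enter a mean under any set, so requiring a recorded time mainly makes the denominator explicit.

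**Conclusion.** The PP set as written cannot do the job the plan gives it for the time endpoint, because it keeps the deviation most able to narrow the difference. If 1-step were truly 1 minute slower, 5–10% wrong-formulation use would raise the one-sided error from 2.5% to 3.7–5.4% (one arm) or 5.4–10.5% (both arms). It would be wrong to read 10.5% as an expected error rate. It needs 10% mix-ups in both arms and a true deficit at the margin; the documents give no mix-up rate, and their procedures suggest a low one. The safety grouping in SAP 3.5 is unclear, though not shown to be contradictory. Both gaps are worth closing before analysis because closing them costs almost nothing.

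**What to change.** **PP set.** In SAP section 2, define PP for the time endpoint as eligible children whose timed dose was prepared with the allocated formulation and has a recorded time with start and stop both observed. Do not exclude preparation errors. Apply the rule to the first dose for the baseline comparison in SAP Table 2, and dose by dose for the comparison using all recorded times. Report PP beside ITT, with the number of doses excluded by arm and reason. A formal requirement that the two agree is optional and is not part of this recommendation.

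**Safety set.** In SAP 3.5, state one population: all children given study drug, grouped by formulation received, with a rule for any child who received both. Remove the ITT sentence or reword it to match.

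**Cost.** A few SAP sentences. The protocol already has the observer record times and vials used, and has all doses entered in the CRF; confirm that the CRF identifies the formulation for each timed dose. The PP set becomes slightly smaller, with power of about 0.93 or 0.92 if 5% or 10% of 100 per arm are removed.

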9.2.2 Proportions

These will be compared using chi squared or Fisher's exact test, as appropriate. Crude proportions will be calculated with the exact 95% confidence intervals (CI), where relevant.

9.2.3 Continuous data

These will be summarised by medians (IQR, ranges) and means (standard deviations, 95% CIs), as appropriate, and will include the parasite counts and laboratory parameters. Comparisons of continuous data will be assessed using the paired/unpaired t tests or the sign rank/Mann Whitney U tests, as appropriate. Analyses of the parasite clearance data will be conducted.

9.2.4 Safety analysis

This is not a study designed chiefly to determine the safety of 1-step artesunate vs conventional 2-step artesunate, as both contain identical drugs. Moreover, this is a small study, and thus the patient populations may vary by chance or by another factor. However, clinical outcome data will be recorded. Safety analyses will be based on the whole population that get administered the study drug. Safety data will be presented in tabular and/or graphical format and summarized descriptively. Any clinically relevant abnormalities or values of potential clinical concern will be described.

Part 2:

All transcripts and the interviewer's notes will be first cross-checked with the audio-recordings. Transcripts and the notes will be coded line by line in qualitative data analysis software NVivo 12 (QSR International, Doncaster, Australia). Coding of data will be based on the initial codebook prepared based on the interview guide (deductive approach) and will be supplemented by revision of codes based on the emerging themes (inductive approach) as the analysis progresses. Two investigators will independently check the coded data against the transcripts. Regular de-briefings will be held between the team members concerning the final themes and their interpretation to reach a consensus. Themes and the supporting quotes will be presented as the findings of this study to address the research question. Survey data will compare the findings between the study staff, and health staff. Differences in acceptability and satisfaction among these two groups of respondents will be evaluated using relevant statistical tests.

Part 3:

In the current study we will focus on the costs of the two different artesunate formulations and the consumables needed for their administration. These direct costs are important at the hospital level, but also for deployment in the wider health system. For example, for the public health system: the shipment cost for the 1-step artesunate will be cheaper than the cost for the conventional 2-step artesunate because the unit volume per pack (box) is smaller for the 1-step artesunate, and lighter.

Finally, using data on the incidence of severe malaria admissions at the sites (primary data) and nationally (national and international annual malaria reports) the total per annum costs of treating patients with the different formulations at the facility and national levels will be estimated.

In the unlikely event that there is an indication of a clinical benefit for the new formulation as compared with the 2-step artesunate, and should it be more costly, we will also perform a cost-effectiveness analysis to determine whether the apparent clinical benefit justifies the incremental cost.

10. DIRECT ACCESS TO SOURCE DATA/DOCUMENTS

Direct access will be granted to authorised representatives from the sponsor and host institutions and the regulatory authorities, if applicable, to permit trial-related monitoring and inspections.

11. QUALITY CONTROL AND QUALITY ASSURANCE PROCEDURES

The study will be conducted in accordance with the current approved protocol, ICH GCP, any national regulations that may apply to this study and standard operating procedures. Regular external monitoring of all sites will be coordinated by the MORU CTSG according to ICH GCP and a Monitoring Plan. Their role will include but not be limited to monitoring adherence to SOPs for collection of clinical data and laboratory specimens and quality checks (curation) of clinical and laboratory data according to standard methodologies.

An online site initiation visit will cover GCP, and study-specific procedures, including: CRF completion, screening and enrolment procedures, data management, follow up scheduling.

11.1. Monitoring

Study sites may have in place a system for internal monitoring. In addition, regular external monitoring of all sites will be performed by the MORU CTSG according to ICH GCP and a Monitoring Plan. Data will be evaluated for compliance with the protocol and accuracy in relation to source documents. The monitors will check whether the clinical trial is conducted and data are generated, documented and reported in compliance with the protocol, GCP and the applicable regulatory requirements.

